12.0 Descriptive Factors

- 12.1 ECOG Performance Status: 0 vs. 1 vs. 2
- 12.2 2^{nd} line vs. $\ge 3^{rd}$ line

13.0 Treatment/Follow-up Decision at Evaluation of Patient

- 13.1 Patients who are CR, PR, or SD will continue treatment per protocol for a maximum of 36 cycles. After 36 cycles, patients will go to event monitoring.
- 13.2 Patients who develop PD while receiving therapy will go to the event-monitoring phase.
- 13.3 Patients who go off protocol treatment for reasons other than PD will go to the eventmonitoring phase per Section 18.0.
- 13.4 Patients who develop non-CNS PD at any time should go to event monitoring. These patients should be treated with alternative chemotherapy if their clinical status is good enough to allow further therapy.
- 13.5 Event monitoring is every 3 months (\pm 14 days) for 5 years after registration. If the patient is still alive 5 years after registration, no further follow up is required.
- 13.6 A patient is deemed *ineligible* if after registration, it is determined that at the time of registration, the patient did not satisfy each and every eligibility criteria for study entry. The patient may continue treatment off-protocol at the discretion of the physician as long as there are no safety concerns, and the patient was properly registered. The patient will go directly to the event-monitoring phase of the study (or off study, if applicable).
 - If the patient received treatment, all data up until the point of confirmation of ineligibility must be submitted. Event monitoring will be required per Section 18.0 of the protocol.

- 13.7 A patient is deemed a *major violation* if protocol requirements regarding treatment in cycle 1 of the initial therapy are severely violated that evaluability for primary end point is questionable. All data up until the point of confirmation of a major violation must be submitted. The patient will go directly to the event-monitoring phase of the study. The patient may continue treatment off-protocol at the discretion of the physician as long as there are no safety concerns, and the patient was properly registered. Event monitoring will be required per Section 18.0 of the protocol.
- 13.8 A patient is deemed a *cancel* if he/she is removed from the study for any reason before any study treatment is given. On-study material and the Off Treatment Form must be submitted.

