2.0 Goals

2.1 Primary Goal

To determine the efficacy of the combination of binimetinib and encorafenib as $\geq 2nd$ line of treatment for patients with metastatic pancreatic cancer with BRAF^{V600E} mutation.

- 2.11 Primary Endpoint Objective response rate at 24 weeks post-registration, as defined by RECIST 1.1.
- 2.2 Secondary Goals To determine in patients treated with the combination of binimetinib and encorafenib as ≥ 2nd line of treatment for patients with metastatic pancreatic cancer with BRAF^{V600E} mutation:
 - 2.21 The median progression-free survival Endpoint: The median time from study registration to clinical or radiographic disease progression or death, whichever occurs first, as defined by RECIST 1.1.
 - 2.22 The median overall survival Endpoint: The median time from study registration to death.
 - 2.23 Duration of Response Endpoint: The median duration of time from first documentation of an objective response to the earliest date progression is documented.
 - 2.24 Time to Response Endpoint: The median duration of time from study registration to the first documentation of an objective response.
 - 2.25 The safety and tolerability Endpoint: The rate of grade 3+ Adverse Events as defined by NIH CTCAE v5.0.
- 2.3 Correlative Research Goal
 - 2.31 To determine the mechanisms of resistance, either primary or acquired through real time monitoring of the BRAF mutational profile evolution.
 - 2.32 Endpoint: Additional mutations in BRAF or in other related genes as determined by nextgeneration sequencing from plasma samples.

3.0 Patient Eligibility NOTE: Waivers to eligibility criteria are not allowed per ACCRU policy

- 3.1 Pre-registration Inclusion Criteria
 - 3.11 Age ≥ 18 years.
 - 3.12 Histological confirmation of a pancreatic malignancy as confirmed by the local pathology lab

- 3.13 Patients whose disease has progressed on (or who were intolerant of) at least one line of therapy for metastatic disease
- 3.14 Patients whose disease has recurred with metastatic disease ≤12 weeks of completion of neoadjuvant or adjuvant systemic chemotherapy; or patients with locally advanced disease whose disease progressed to metastatic disease on, or ≤12 weeks after completion of systemic chemotherapy would also be eligible
- 3.15 Provide informed written consent ≤ 28 days prior to pre-registration.

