16.3 Analysis Plan

16.31 Primary Endpoint Analysis

The analysis for this trial will begin at planned time points (see 16.2) and at the time the patients have become evaluable for the primary endpoint. Such a decision will be made by the statistician and Study Chair, in accord with CCS Standard Operating Procedures, availability of data for secondary and correlative endpoints, and the level of data maturity.

16.311 Definition

The primary endpoint for this study is defined in section 16.21. The final ORR point estimate and corresponding 95% confidence interval will be reported.

16.312 Estimation

The proportion of successes will be estimated by the number of successes divided by the total number of evaluable patients. Confidence intervals for the true success proportion will be calculated according to the approach of Clopper and Pearson.

16.313 Over Accrual

If more than the target number of patients are accrued, the additional patients will not be used to evaluate the stopping rule or used in any decision making process. However, they will be included in final point estimates and confidence intervals as though they were accrued in the final stage.

- 16.32 Secondary Endpoint Analysis
 - 16.321 Progression-Free Survival

Progression-free survival (PFS) is defined as the time from registration to the first of either disease progression or death from any cause, where disease progression is determined based on RECIST 1.1 criteria. PFS will be estimated using the Kaplan-Meier method. The median PFS and corresponding 95% confidence interval will be reported. Patients who do not experience disease progression or death while on protocol will be censored at the last disease assessment date.

16.322 Overall Survival

Overall survival (OS) is defined as the time from registration to death from any cause. Analysis of this endpoint will mirror that of PFS (section 16.321).

16.323 Duration of Response

Duration of response is defined as the duration of time from first documentation of an objective response (defined in 16.21) to the earliest date disease progression is documented or death from any cause. Analysis of this endpoint will mirror that of PFS (Section 16.321).

16.324 Time to Response

Time to response is defined as the duration of time from registration to the first documentation of an objective response (defined in 16.21). Analysis of this endpoint will mirror that of PFS (section 16.321).

16.325 Adverse Event Rate

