	Event Monitoring Phase ¹				
CRF	q. 3 months until PD	At PD	After PD q. 3 mos.	Death	
Patient Status: Survival and Disease Status Follow-Up/Event Monitoring	X^2	X^2	Х	Х	
Adverse Events: Late ³					
Supporting Documentation ^{2, 3}					
Consent Withdrawal (choose					
appropriate form) ³					
 Consent Withdrawal: Specimen 					
Only					
• Consent Withdrawal: All Follow-Up					
Lost to Follow-Up ^{3,4}					
ACCRU Deviation Form ³	X^3	X ³	X ³	X^3	

1. If a patient is still alive 5 years after registration, no further follow-up is required.

2. Upload a copy of documentation of response or progression in RAVE on the Supporting Documentation Form.

- 3. Submit only if applicable.
- 4. Patients are eligible to be confirmed lost to follow-up after 2 years of unsuccessful contact with the patient.

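### Section 16.321 defines PFS by any progression or death, then censors patients with no event while on protocol, an undefined term that OS and duration of response inherit

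*Combined protocol and SAP*

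**What the plan says.** **Definition.** Section 16.321: "Progression-free survival (PFS) is defined as the time from registration to the first of either disease progression or death from any cause". Section 2.21 likewise runs to "clinical or radiographic disease progression or death, whichever occurs first, as defined by RECIST 1.1". Neither limits the endpoint to time on treatment.

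**Censoring.** The last sentence of Section 16.321: "Patients who do not experience disease progression or death while on protocol will be censored at the last disease assessment date". The documents do not define *on protocol*.

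**Other endpoints.** Section 16.322: "Overall survival (OS) is defined as the time from registration to death from any cause. Analysis of this endpoint will mirror that of PFS". Section 16.323 gives duration of response the same treatment.

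**Follow-up.** Section 13.3: "Patients who go off protocol treatment for reasons other than PD will go to the eventmonitoring phase per Section 18.0". Section 13.2 sends patients with progression to the same phase. Under Section 13.5 event monitoring runs every 3 months "for 5 years after registration. If the patient is still alive 5 years after registration, no further follow up is required". The follow-up table in Section 18.1 collects the survival and disease status form "q. 3 months until PD", at progression, afterwards, and at death, and asks for documentation of progression to be uploaded.

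**Imaging.** The test schedule in Section 4.0 has imaging on treatment and at progression, withdrawal or removal, with no event-monitoring column. Section 11.1 sets re-evaluation every 8 weeks without saying whether this ends when treatment stops.

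**The concern.** The definition and the censoring sentence in Section 16.321 give different answers for the same patient. Someone who stops for toxicity, enters event monitoring without progression and then progresses or dies has a PFS event under the definition. Under the censoring sentence, if *on protocol* means on protocol treatment, that patient is censored at the last disease assessment and the recorded event is not used.

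For PFS and duration of response, the risk is informative censoring: patients who stop early may differ in prognosis from those who continue. For OS the effect could be larger, because patients with progression also move to event monitoring and many deaths will be recorded there. A literal mirror of the rule would drop them. Time-to-event results in a single-arm trial will be read against outside benchmarks, such as the 4-month median PFS that Section 1.11 gives for the approved second-line regimen, so the rule should have one meaning before the data are analysed.

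**Working it through.** **1. What each reading does.**

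| Patient | *On protocol* = on protocol treatment | *On protocol* = on study, including event monitoring |
|---|---|---|
| Non-PD stop, later progression or death | PFS censored at last assessment, against the definition | PFS event |
| Progression on treatment, later death | OS censored if the rule is mirrored | OS event |
| Alive in event monitoring | OS censored at last disease assessment | OS censored at last disease assessment |

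The last row is wrong under both readings if the mirrored analysis includes the censoring rule, because quarterly survival contacts continue after disease assessments end. The OS errors run in opposite directions. Dropping deaths raises estimated OS. Counting all deaths while cutting survivors' follow-up short removes survivors from the risk set and lowers it.

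**2. Size for PFS.** The plan states no PFS target, event count or power, so there is no figure to reproduce.

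Inputs:
- Median PFS under censoring at the stop, m = 4.0 months. This borrows the Section 1.11 figure as a reference value.
- Share s of on-treatment exits that are non-PD stops: not in the documents, assumed 10%, 20%, 30%.
- Hazard after the stop relative to on treatment, k: not in the documents, assumed 0.5 to 3.
- Exponential times, with the last assessment at the stop.

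Formulas:
- λ = ln 2 / m
- g = λs/(1 − s), the stop hazard
- Censoring at the stop: S(t) = exp(−λt), median m
- Counting all events: S(t) = exp(−(λ+g)t) + g[exp(−kλt) − exp(−(λ+g)t)]/(λ + g − kλ)

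Example, s = 20% and k = 2: λ = 0.6931/4 = 0.1733; g = 0.1733 × 0.2/0.8 = 0.0433; λ+g = 0.2166; kλ = 0.3466. At t = 3.76, S = 0.443 + 0.0433 × (0.272 − 0.443)/(0.2166 − 0.3466) = 0.443 + 0.057 = 0.500. The all-event median is 3.76, so censoring overstates it by 4.00 − 3.76 = 0.24 months.

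All-event median in months (overstatement by censoring in brackets):

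| s | k = 0.5 | k = 1 | k = 2 | k = 3 |
|---|---|---|---|---|
| 10% | 4.09 (−0.09) | 4.00 (0) | 3.88 (0.12) | 3.81 (0.19) |
| 20% | 4.20 (−0.20) | 4.00 (0) | 3.76 (0.24) | 3.62 (0.38) |
| 30% | 4.35 (−0.35) | 4.00 (0) | 3.62 (0.38) | 3.42 (0.58) |

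For k = 2 to 3 this is 3% to 17% of the all-event median. The percentages are the same for a 2-month median.

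**3. Effect of 3-monthly dating.** A simulation of 26 patients (3,000 runs, same model) dated each post-stop event at the next 3-monthly contact. At s = 20%:

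| k | All events, exact dates | Censored at stop | All events, 3-monthly dates |
|---|---|---|---|
| 1 | 3.82 | 4.02 | 4.04 |
| 2 | 3.54 | 3.99 | 3.92 |
| 3 | 3.43 | 3.96 | 3.84 |

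These small-sample medians differ from the closed form (3.82 against 4.00 at k = 1), so compare only within a row. Over s = 10% to 30% and k = 1 to 3, coarse dating added about 0.1 to 0.7 months to the exact-date median. That is near an upper limit, because deaths would carry exact dates and the comparison uses exact event times.

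**The case against.** The best defence is that *on protocol* means on study. Section 13.3 speaks of leaving protocol treatment, whereas Section 16.321 does not say treatment. Section 13.6 treats event monitoring as a phase of the study and contrasts it with being off study. That reading agrees with the PFS definition. The treatment-only reading would remove most deaths from OS, which cannot be intended, and *mirror* may mean only Kaplan-Meier, the median and its interval.

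This makes the treatment-only reading less likely but does not exclude it. Sections 13.6 and 13.7 both say "The patient may continue treatment off-protocol at the discretion of the physician as long as there are no safety concerns" of patients who are in event monitoring. There the phrase describes treatment, and a programmer could apply the same sense to Section 16.321. If *mirror* excludes the censoring rule, OS has no stated censoring rule at all.

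Three stronger inferences are tempting but not supported:

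- *PFS counts only on-treatment events, and no tumour assessment follows a non-PD stop.* The first is one reading of an undefined term. On the second, Section 4.0 schedules imaging at withdrawal or removal, Section 11.1 does not end re-evaluation at the stop, and disease status is collected quarterly.
- *The clause must lengthen median PFS.* It does so only if hazard rises after the stop. Section 11.45 already reports stops for symptomatic deterioration as PD, so some of the most prognosis-related stops are events and are not censored.
- *The inflation is large.* Censoring a random 10%, 20% or 30% of events at the last 8-weekly scan before the event turns a true 4.0 months into about 4.4, 4.8 or 5.5. That calculation contains no treatment stop: it places every censored patient within 8 weeks of the event and keeps scans running up to it.

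It also stands that these are descriptive secondary endpoints, with no test or decision rule, in a trial of 26 evaluable patients.

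**Conclusion.** The point holds as an internal contradiction with a specified remedy. Section 16.321 defines PFS without a treatment limit and then censors by a term that can impose one. On the treatment-only reading, data the trial deliberately collects would be discarded for PFS and duration of response, and deaths after treatment could be lost from OS. On either reading of *on protocol*, carrying the rule to OS censors living patients at the wrong date.

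Neither the direction nor the size of the PFS bias can be read from the documents. Under the stated assumptions (exponential times, 10% to 30% non-PD stops, censored median 4.0 months), it is nil at unchanged post-stop hazard, about 0.1 to 0.6 months upward at two- to threefold hazard, and 0.1 to 0.35 months downward at half the hazard. The treatment of symptomatic deterioration as PD limits it further. The primary endpoint is not touched. The wording should be corrected before analysis, but the trial's main conclusion does not depend on it.

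**What to change.** - **Section 16.321:** replace *while on protocol* with *during active or event monitoring*. Count the first progression or death recorded at any time in those phases. Censor only patients who are alive and progression-free, at their last disease assessment.
- **Section 16.323:** apply the same rule to duration of response.
- **Section 16.322:** give OS its own rule, with censoring at the date last known alive.

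As worded, events after a later anticancer therapy would count. If the sponsor wants otherwise, the section should say so.

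The change is to SAP text only. It needs no extra scans or forms, because Section 18.1 already collects the data. The downside is that progressions found in event monitoring may be dated on a 3-month grid. The simulation shows that this can offset much of the gain in the median if every such event is dated at the contact, so the date shown in the uploaded progression documentation should be used where there is one. Deaths and OS do not have this problem.

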14.0 Body Fluid Biospecimens

- 14.1 Blood/Blood Products Handling
 - 14.11 Kits are required for this study.

14.111 The kit contains supplies and instructions for collecting, processing, and shipping specimens.

- 14.112 Participating institutions may obtain kits by completing and faxing the Supply Order Form (found in the Forms Packet) to the number listed on the form. Fill out the site address to where the kits will be shipped on the Fax Supply form. Because we are now being charged for all outgoing kits, a small, but sufficient, supply of the specimen collection kits should be ordered prior to patient entry. Do not send the unused kits back to Biospecimen Accessioning and Processing (BAP) Receiving or the BAP Shared Resource. Note: Expired tubes may be replaced with site stock if available.
- 14.113 Kits will be sent via FedEx® Ground at no additional cost to the participating institutions. Allow at least two weeks to receive the kits. Kits will arrive inside the shipping boxes.
- 14.114 Kits will not be sent via rush delivery service unless the participating institution provides their own FedEx® account number or alternate billing number for express service. ACCRU will not cover the cost for rush delivery of kits.
- 14.12 All samples must be collected Monday-Friday ONLY.
- 14.13 Label specimen tube(s) with protocol number, ACCRU patient ID number, and time and date blood is drawn.
- 14.14 Collect and process all blood/blood products according to specific kit instructions and table below.
 - 14.241 Summary Table of Research Blood/Blood Products to Be Collected for

This Protocol

Indicate if specimen is mandatory or optional	Collection tube description and/or additive (color of tube top)	Volume to collect per tube (number of tubes to be collected)	Blood product being processed and submitted by participating site	Baseline Prior to Treatment	Every 4 weeks Prior to Treatment	Off study or Progre ssion	Additional processing required at site after blood draw?	Storage /shipping conditions ¹
Mandatory	STRECK (black/tan)	10 ml (2)	Platelet poor plasma	X	X	X	No	Ambient (room tempera-
								ture cold packs)
Mandatory	EDTA (purple top)	10mL (2)	Plasma and White Blood Cells (buffy coat)	X	X	X	No	Refrig- erate (cold packs)

1. After all samples have been processed according to kit instructions, ship all specimens According to shipping instructions (see Section 14.25 for detailed shipping instructions.)

2. Blood draws should not be collected and submitted until after the patient is registered onto the study.

- 14.15 Shipping
 - 14.151 Verify ALL sections of the Blood Specimen Submission Form (see Forms Packet), BAP Requisition Form (provided in kit) *(if applicable)*], and specimen collection labels are completed and filled in correctly.
 - 14.152 Specimens must be shipped the same day they are drawn.
 - 14.153 Specimens will be shipped in a dual-temperature shipping container. Place the refrigerated EDTA tubes with a properly prepared cold pack in one compartment. See kit instructions for specific details for cold pack preparation (i.e., frozen or refrigerated) and proper packing of blood and cold pack to avoid freezing of specimen. Place the STRECK tubes with an ambient cold pack in the other compartment of the dual-temperature shipping container.
 - 14.154 Ship specimens via Priority Overnight service, Monday Friday ONLY, to BAP Receiving according to kit instructions. Do not send samples on weekends or just prior to federal holidays.
 - 14.155 The BAP kits will include a smart shipper label (3x5 white barcoded label) affixed to the shipping boxes. The smart shipper label is a preaddressed return label, which replaces the need for an airbill. Shipping costs will be covered by ACCRU if the shipping box provided with the BAP kit is used for shipping specimens to BAP Receiving.

Ship blood samples to:

BAP Freezer will receive the samples for ACCRU.

- 14.2 Study Methodology and Storage Information
 - 14.21 Blood/blood product samples will be collected for the following research
 - 14.211 DNA extraction and storage of DNA for future research (e.g., for genetic polymorphisms or cfDNA sequence and analysis) Plasma/cells/DNA will be stored frozen at -70°C by BAP and at the end of the trial all specimens will be sent to Dana-Farber Cancer Institute, according to patient consent information (see Section 6.22) until specific analyses are identified. As protocols are developed, they will be presented for ACCRU and IRB review and approval. (This collection is part of a general strategy of investigation for the majority of ACCRU studies.)

ACCRU will ship samples to:

14.212 As part of ongoing ACCRU research, we will collect plasma for future research studies, according to patient consent information (see Section 6.24), on molecular determinants of efficacy and tolerability. Samples will be stored frozen at -70°C by BAP until specific analyses are identified. As protocols are developed, they will be presented for ACCRU and IRB review and approval.

14.3 Return of Genetic Testing Research Results

Because the results generated by the genetic testing included in this section are not currently anticipated to have clinical relevance to the patient or their family members, the genetic results will not be disclosed to the patients or their physicians.

If, at any time, genetic results are obtained that may have clinical relevance, IRB review and approval will be sought regarding the most appropriate manner of disclosure and whether or not validation in a CLIA-certified setting will be required. Sharing of

research data with individual patients should only occur when data have been validated by multiple studies and testing has been done in CLIA-approved laboratories.

15.0 Drug Information

IND exempt

• Investigator brochure available on the ACCRU website.

15.1 Binimetinib (MEK162, ARRY-438162, ONO-7703)

- 15.11 **Background**: Binimetinib is an orally bioavailable, selective and potent MEK1 and MEK 2 inhibitor. As a MEK inhibitor, this compound has the potential to benefit patients with advanced cancers by inhibiting the MAPK (mitogen-activated protein kinases) pathway.
- 15.12 **Formulation**: Binimetinib drug product is supplied as film-coated tablets in a dose strength of 15 mg. The film coated-tablets consist of binimetinib, colloidal silicon dioxide/silica colloidal anhydrous; croscarmellose sodium; lactose monohydrate; magnesium stearate; microcrystalline cellulose/cellulose, microcrystalline; and a commercial film coating. The tablet is ovaloid biconvex (capsule shaped), yellow to dark yellow in color.
- 15.13 **Preparation and storage**: Binimetinib film-coated tablets should not be stored above 25°C and should be protected from light. Tablets are packaged in plastic bottles acceptable for pharmaceutical use.
- 15.14 **Administration:** Binimetinib is administered twice daily with water, approximately 12 hours apart with or without meals. Tablets should be swallowed whole and should not be chewed.

15.15 **Pharmacokinetic information**:

Absorption: The pharmacokinetics of binimetinib are characterized by moderate to high variability, accumulation of approximately 1.5-fold, and steady state concentrations reached within 15 days. The human ADME study CMEK162A2102 indicated that approximately 50% of binimetinib dose was absorbed.

Distribution: Binimetinib is more distributed in plasma than blood. The blood-to-plasma concentration ratio of binimetinib in humans is 0.718. It is highly bound to plasma proteins (humans: 97.2%).

Metabolism: The primary metabolic pathways include glucuronidation (up to 61.2% via UGT1A1), N-dealkylation (up to 17.8% via CYP1A2 and CYP2C19) and amide hydrolysis.

Excretion: The excretion route was 31.7% of unchanged binimetinib in feces and 18.4% in urine. Estimated renal clearance of unchanged binimetinib was 6.3% of total dose.

15.16 **Potential Drug Interactions**:

Overall, the risk for binimetinib to be a cause of or be affected by significant drug-drug interactions is predicted to be low. However, given the predominant role of UGT1A1 in the metabolism of binimetinib, and because the effect of a UGT1A1 inhibitor or inducer has not been evaluated in a formal clinical study, special consideration should be taken for co-administration of drugs that are UGT1A1 inhibitors or inducers, and administration of binimetinib to patients with low UGT1A1 activity.

Binimetinib has been shown to be a substrate for P-gp and BCRP in vitro. The impact of P-gp/BCRP inhibitors on the PK of binimetinib in vivo is unknown; therefore, it is recommended that P-gp and BCRP inhibitors are dosed with caution.

15.17 Known potential toxicities:

Very Common (\geq 10%) - diarrhea, nausea, vomiting, fatigue, peripheral edema, increased AST, increased blood creatine phosphokinase, dermatitis acneiform, dry skin, pruritus, rash, decreased ejection fraction

Common ($\geq 1\%$ - <10%) - chorioretinopathy, dry eye, macular edema, retinal detachment, retinal vein occlusion, retinopathy, serous retinal damage, blurred vision, reduced visual acuity, visual impairment, abdominal pain, constipation, dyspepsia, gastroesophageal reflux disease, asthenia, facial edema, edema, malaise, pyrexia, folliculitis, paronychia, pustular rash, increased ALT, increased amylase, increased blood alkaline phosphatase, increased blood creatinine, increased GGT, lipase increased, arthralgia, muscular weakness, myalgia, dizziness, dysgeusia, epistaxis, alopecia, xerosis, nail disorder, palmar-plantar erythrodysesthesia syndrome, eczema, erythema, erythematous rash, papular rash, macular rash, maculo-papular rash, skin fissures, hypertension, neutropenia, pneumonitis

Uncommon (≥0.1 - <1%) – anemia, left ventricular dysfunction, eye edema, gastritis, gastrointestinal hemorrhage, colitis, general physical health deterioration, infection, skin infection, cellulitis, erysipelas, irregular heart rate, hypoglycemia, musculoskeletal pain, rhabdomyolysis, dropped head syndrome, ageusia, pulmonary embolism, xeroderma, follicular rash, pruritic rash, deep vein thrombosis, hypertensive crisis, hypotension

15.18 Nursing Guidelines:

- 15.181 Agent can cause decreased LVEF function. Instruct patients to report any lower extremity swelling, shortness of breath, and/or chest pain to study team.
- 15.182 Diarrhea and other gastrointestinal side effects are common. Treat symptomatically and monitor for effectiveness of intervention.
- 15.183 Rash is common and is usually acneiform in nature. Instruct patient to report any rash immediately.
- 15.184 Bleeding including serious and/or fatal hemorrhage can be seen. Instruct patient to report any bleeding to study team.

- 15.185 Monitor LFT's.
- 15.186 Rarely interstitial lung disease can be seen. Instruct patient to report any cough, dyspnea to the study team.
- 15.187 Rhabdomyolysis is a rare but serious side effect of this agent. Instruct patients to report any weakness, muscle pain, or just feelings or unwellness to the study team immediately.
- 15.188 Rarely ocular complications can occur, including chorioretinopathy, serous retinal damage, retinal detachment and other visual disturbances. Instruct patients to report any visual disturbances and/or eye pain to the study team immediately.
- 15.189a Strenuous physical activities, such as competitive sports, can results in significant increases in CK levels while on binimetinib treatment. Instruct patients to not start a new strenuous exercise regimen after first dose of study treatment.
- 15.19a **Drug procurement:** Drug procurement: Array BioPharma, Inc will supply the drug to Clinical Research Services, a division of Rx Crossroads by McKesson. Each participating ACCRU treating location will order the drug from Clinical Research Services, a division of Rx Crossroads by McKesson. Submit the Drug Order Request Form (found on the ACCRU web site) to:

Each participating ACCRU treating location will be responsible for monitoring the supply of binimetinib and will use the Drug Order Request Form to order additional supplies as needed.

Outdated or remaining drug is to be destroyed on-site as per procedures in place at each institution.

- 15.19bTemperature excursions that occur at the site should be reported by the site to Clinical Research Services, a division of Rx Crossroads by McKesson via email to: Any shipment deviations (those not occurring at the site) should be reported to Clinical Research Services, a division of Rx Crossroads by McKesson, via email to: Clinical Research Services, a division of Rx Crossroads by McKesson, will report any temperature and shipment deviations (those not occurring at the site) to Array BioPharma Inc. via email to:
 - 15.19b1When reporting a temperature excursion to Clinical Research Services, please include the following information as required by Array:

- Study/protocol number
- Name and contact information
- Site location and address
- Array lot and kit numbers affected (if applicable)
- High/low temperature recorded for event
- Duration of the event
- All supporting data or charts (Temp Log, TempTale, etc.)
- Temperature deviation event form (if site has their own)

Following temperature deviation, the affected material should be physically quarantined by the site until a response is received from Array regarding the disposition of the affected materials.

15.2 Encorafenib (LGX818, ONO-7702, Braftovi®):

- 15.21 **Background:** Encorafenib is a potent and selective ATP-competitive inhibitor of BRAF V600-mutant kinase.
- 15.22 **Formulation**: The encorafenib drug product is supplied as a hard gelatin capsule in dosage strengths 75 mg. The dosage forms for each strength have identical formulations which are packaged in different colored capsules:
 - 75 mg capsule (FMI): Size #00 hard gelatin capsules; flesh opaque cap and white opaque body, with the markings "NVR" or stylized "A" on the cap and "LGX 75mg" on body.

The capsules consist of encorafenib drug substance, copovidone, poloxamer 188, succinic acid, microcrystalline cellulose, colloid silicon dioxide, crospovidone, and magnesium stearate of vegetable origin.

- 15.23 **Preparation and storage**: Encorafenib hard gelatin capsules should not be stored above 25°C and should be protected from moisture. Capsules are packaged in plastic bottles acceptable for pharmaceutical use and should not be repackaged at the site.
- 15.24 Administration: Encorafenib capsules are intended for oral administration with water; capsules should be swallowed whole and should not be chewed. Encorafenib capsules may also be opened and the powder mixed with sweetened applesauce; the soft food preparation is intended for oral administration with water. Encorafenib can be administered without regard to food.

15.25 **Pharmacokinetic information**:

Absorption: At least 86% of the dose is absorbed Metabolism: N-dealkylation is the primary metabolic pathway; CYP3A4 (primary), CYP2C19, and CYP2D6 (minor) contribute to total oxidative clearance in human liver microsomes Half-life elimination: 6.32 hours (range 3.74 to 8.09 hours) Excretion: Feces (39%); urine (47.2%)

15.26 **Potential Drug Interactions**:

Since encorafenib is mainly metabolized by CYP3A, the co-administration of CYP3A inducers might decrease the exposure of encorafenib in clinical practice. Thus, long term co-administration of strong and moderate inducers of CYP3A with encorafenib should be avoided.

Clinical results from a dedicated DDI study with encorafenib and CYP3A inhibitors indicated concomitant administration of encorafenib with strong or moderate CYP3A inhibitors may increase encorafenib plasma concentration. If co-administration with strong or moderate CYP3A inhibitors cannot be avoided, dose reduction of encorafenib may be warranted.

Since no clinical data are available, caution should be used for coadministering substrates of CYP3A4 and UGT1A1.

Based on in vitro transporter studies, encorafenib can potentially inhibit the transporters P-gp, BCRP, OATP1B1, OATP1B3, OAT1, OAT3 and OCT2 at clinical concentrations. Co-administration of encorafenib with drugs that are substrates for these enzymes and/or transporters may alter the exposure of the co-administered medication.

15.27 Known potential toxicities:

Verv Common (≥10%) Gastrointestinal: diarrhea Metabolism and nutrition: decreased appetite Nervous system: peripheral neuropathy Psychiatric: insomnia Skin and subcutaneous: hair loss, dry skin, hyperkeratosis, pruritis, Palmarplantar erythrodysesthesia syndrome, palmoplantar keratoderma, erythema Vascular: flushing Common (≥1% - <10%) Blood and lymphatic: anemia Cardiac: tachycardia Ear and labyrinth: vertigo Eye: iridocyclitis Gastrointestinal: nausea, vomiting, abdominal pain, constipation, dyspepsia, stomatitis General: asthenia, fatigue, pyrexia, xerosis, chills, face edema, peripheral edema Immune system: hypersensitivity Investigations: AST and ALT increased, blood alkaline phosphatase increased, blood creatinine increased, gamma-glutamyltransferase increased, amylase increased, lipase increased, electrocardiogram QT prolonged Metabolism and nutrition: dehydration, hyponatremia Musculoskeletal and connective tissue: arthralgia, musculoskeletal pain, myalgia, muscle spasms, muscular weakness Neoplasms benign, malignant and unspecified: keratoacanthoma, melanocytic nevus, skin papilloma, squamous cell carcinoma, dysplatic nevus, malignant melanoma Nervous system: facial paralysis, facial paresis, ageusia, dysgeusia, dysesthesia, hyperesthesia, neuralgia

Renal and urinary: acute kidney injury, renal failure Skin and subcutaneous: rash, photosensitivity reaction, skin exfoliation, skin hyperpigmentation Uncommon (≥0.1% - <1%) Eye: uveitis Gastrointestinal: pancreatitis Metabolism and nutrition: hyperglycemia Musculoskeletal and connective tissue: back pain, pain in extremity Neoplasms benign, malignant and unspecified: acanthoma, basal cell carcinoma Nervous system: hypoaesthesia Skin and subcutaneous: drug eruption, urticarial

15.28 Nursing Guidelines:

- 15.281 Diarrhea and nausea are common. Treat symptomatically and monitor for effectiveness.
- 15.282 Warn patients of possibility of secondary skin cancers. Instruct patients to report any new lesions to study team immediately.
- 15.283 Monitor LFT's, especially in combination therapy.
- 15.284 Agent may cause arthralgias. Treat symptomatically and monitor for effectiveness.
- 15.285 Agent causes QTc prolongation. Instruct patients to discuss any new medications with the study team, prior to starting such agents.
- 15.286 Agent can cause peripheral edema.
- 15.287 Rarely ocular toxicity can occur including retinitis, uveitis, and retinal vein occlusion. Instruct patients to report any vision changes and/or eye pain to the study team.
- 15.288 Monitor renal function, encourage patients drink adequate fluids.
- 15.289aRash can be seen. Instruct patient to report rash to study team.
- 15.289bAgent can cause pyrexia, especially in combination with binimetinib. Instruct patient to report any fever to the study team.
- 15.29a **Drug procurement:** Drug procurement: Array BioPharma, Inc will supply the drug to Clinical Research Services, a division of Rx Crossroads by McKesson. Each participating ACCRU treating location will order the drug from Clinical Research Services, a division of Rx Crossroads by McKesson. Submit the Drug Order Request Form (found on the ACCRU web site) to:

Clinical Research Services, a division of Rx Crossroads by McKesson

Each participating ACCRU treating location will be responsible for monitoring the supply of encorafenib and will use the Drug Order Request Form to order additional supplies as needed.

Outdated or remaining drug is to be destroyed on-site as per procedures in place at each institution.

15.29b Temperature excursions that occur at the site should be reported by the site to Clinical Research Services, a division of Rx Crossroads by McKesson via email to: Any shipment deviations (those not occurring at the site) should be reported to Clinical Research Services, a division of Rx Crossroads by McKesson, via email to:

Clinical Research Services, a division of Rx Crossroads by McKesson, will report any temperature and shipment deviations (those not occurring at the site) to Array BioPharma Inc. via email to:

15.29b1When reporting a temperature excursion to Clinical Research Services,

- please include the following information as required by Array:
 - Study/protocol number
 - Name and contact information
 - Site location and address
 - Array lot and kit numbers affected (if applicable)
 - High/low temperature recorded for event
 - Duration of the event
 - All supporting data or charts (Temp Log, TempTale, etc.)
 - Temperature deviation event form (if site has their own)

Following temperature deviation, the affected material should be physically quarantined by the site until a response is received from Array regarding the disposition of the affected materials.

